5.5. Disease Stage

The international staging system (see Table 2) for multiple myeloma will be applied for patient classification at baseline.

Table 2: International Staging System for Multiple Myeloma

Stage	Criteria
I	Serum β_2 -micoglobulin < 3.5 mg/L and serum albumin \geq 3.5 g/dL
II	Not Stage I or III (Serum β_2 -micoglobulin < 3.5 mg/L and serum albumin < 3.5 g/dL; or Serum β_2 -micoglobulin 3.5 to <5.5 mg/L irrespective to the serum albumin level)
III	Serum β_2 -micoglobulin \geq 5.5 mg/L

5.6. ECOG and Karnofsky Performance Status Scores

For subjects in Cohort 1, Karnofsky performance status scores are measured and recorded according to the original protocol dated November 4, 2011. For those subjects, the ECOG performance status will be derived from Karnofsky performance scores (see Table 3).

Under protocol amendment 1, the decision was made to collect ECOG performance status rather than Karnofsky performance status for all subjects enrolled afterwards.

Table 3: ECOG and Karnofsky Performance Status Scores

Karnofsky Performance Status (%)	ECOG Performance Status
90, 100	0
70, 80	1
50, 60	2
30, 40	3
10, 20	4
0	5

5.7. Treatment-Emergent Period

The treatment-emergent period is defined as the period of time from the date of the first dose of study drug through 30 days after the date of the last dose of study drug (ibrutinib or dexamethasone) or the day before initiation of any subsequent anti-myeloma therapy, whichever occurs first.

The treatment-emergent period for monotherapy (Cohorts 1 and 3 only) is defined as the period of time from the date of the first dose of ibrutinib through 30 days after the date of the last dose of ibrutinib, or the day before the addition of dexamethasone, or the day before initiation of any subsequent anti-myeloma therapy, whichever occurs first.

5.8. Average Dose and Relative Dose Intensity

For ibrutinib:

Average dose administered (mg/day) = total cumulative dose administered (mg) / treatment duration (day) for ibrutinib.

For dexamethasone:

Average dose administered (mg/week) = total cumulative dose administered (mg) / treatment duration (week) for dexamethasone.

Total cumulative dose administered is the sum of dose actually taken during the treatment period. Relative dose intensity is defined as the percentage of the total expected dose that was actually administered.

Relative dose intensity (%) = total cumulative dose administered / total expected dose × 100%.

For ibrutinib:

Total expected dose (mg) = treatment duration (day) for ibrutinib × protocol assigned daily dose (e.g. 420 mg/day for Cohort 1).

For dexamethasone:

Total expected dose (mg) = treatment duration (week) for dexamethasone × protocol assigned weekly dose (40 mg/week).

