### 6.3.2 Dexamethasone

Subjects receiving dexamethasone will receive 40 mg orally once per week. Dexamethasone may be taken as either a single dose in the morning or as divided doses over the course of the day.

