5. ANALYTIC DEFINITIONS

5.1. Study Day and Duration of Treatment

Study day will be calculated in reference to the date of the first dose of study drug. Study Day 1 corresponds to the date the subject received the first dose of study drug. For assessments/events occurred on or after Study Day 1, study day is calculated as (assessment/event date – date of the first dose of study drug + 1 day). For assessments/events occurred prior to Study Day 1, study day is calculated as (assessment/event date – date of the first dose of study drug). Study Day –1 is the day before Study Day 1. There will not be a Study Day 0.

Treatment duration for ibrutinib will be calculated as the interval from the date of the first dose of ibrutinib to the date of the last dose of ibrutinib. Similarly, treatment duration for dexamethasone will be calculated.

Treatment duration (day) = date of the last dose – date of the first dose + 1 day

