5.10. Other General Definitions

Age:

Age in years will be calculated at the date of informed consent.

Conversions:

- 1 month = 30.4375 days.
- 1 year = 365.25 days.

6. Missing Data Handling

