8.6. Study Drug Exposure

Ibrutinib and/or dexamethasone dose for a subject may be held and/or reduced according to the protocol specified criteria (see protocol Section 6.5).

For each subject the following parameters will be calculated when applicable.

- Treatment duration for each study drug (ibrutinib or dexamethasone) in month
- Time to addition of dexamethasone in month (Cohorts 1 and 3 only)
- Total cumulative dose administered for each study drug
- Average dose administered for each study drug

-
- Relative dose intensity for each study drug
 - Number of dose missed for each study drug
 - Number of dose reduction for each study drug
 - Ibrutinib dose interruption ≥ 7 consecutive days (yes or no)
 - Dexamethasone dose interruption ≥ 14 consecutive days (yes or no)

For each parameter, descriptive statistics (mean, standard deviation, median, and range for continuous variables; number and proportion for categorical variables) will be calculated by treatment cohort.

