8.9. Safety Analyses

All safety analyses will be based on the safety population.

In Cohorts 1 and 3, subjects will be on ibrutinib monotherapy and may convert to ibrutinib and dexamethasone combination therapy at the discretion of the investigator after a confirmed PD on ibrutinib monotherapy. Thus the safety data (e.g. incidence of TEAEs, laboratory values) will be presented and distinguished as with and without dexamethasone for subjects in Cohorts 1 and 3, when applicable.

Table 7: Summary of Safety Analyses to be Performed

Category	Analysis	Summarize By	Listing
Adverse Events			
General	Overall summary	Study Period	
	TEAEs	SOC+ PT+Study Period; PT+ toxicity grade+Study Period	
	Grade 3 or worse TEAE	SOC+ PT+Study Period; PT+ toxicity grade+Study Period	
	Ibrutinib Related TEAE	SOC+ PT (Whole Study Period only)	
	Dexamethasone Related TEAE	SOC+ PT (Whole Study Period only)	
	Grade 3 or worse Ibrutinib Related TEAE	SOC+ PT (Whole Study Period only)	
	Grade 3 or worse Dexamethasone Related TEAE	SOC+ PT (Whole Study Period only)	
	TEAEs leading to treatment discontinuation		✓
	TEAEs leading to Ibrutinib discontinuation	SOC+ PT (Whole Study Period only)	
	TEAEs leading to Dexamethasone discontinuation	SOC+ PT (Whole Study Period only)	
	TEAEs leading to dose reduction or dose withheld		✓
	TEAEs leading to Ibrutinib dose reduction	SOC+ PT+Study Period	
	TEAEs leading to Dexamethasone dose reduction	SOC+ PT+Study Period	
	TEAEs leading to Ibrutinib dose withheld	SOC+ PT+Study Period	
	TEAEs leading to Dexamethasone dose withheld	SOC+ PT+Study Period	
	Serious TEAEs	SOC+ PT + Study Period; PT + toxicity grade + Study Period	✓
	Ibrutinib Related Serious TEAEs	SOC+ PT (Whole Study Period only)	
	Dexamethasone Related Serious TEAEs	SOC+ PT (Whole Study Period only)	
	Treatment emergent bleeding events	PT + toxicity grade+Study Period	

Category	Analysis	Summarize By	Listing
	Treatment emergent major hemorrhage	PT + toxicity grade+Study Period	✓
	Treatment emergent atrial fibrillation and atrial flutter events		✓
Death	Death within 30 days of last study treatment	Whole Study Period	
	All Deaths		✓
Laboratory Evaluations			
Hematology	Measured values and change from baseline	Visit+Study Period	
	Treatment emergent worst post-baseline low abnormalities	Toxicity grade+Study Period	
	Shift of toxicity grade in low direction	Toxicity grade+Study Period	
Chemistry	Measured values and change from baseline	Visit+Study Period	

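### For weekly dexamethasone, the SAP's exposure formulas leave out six of the seven days covered by the last dose, so average weekly dose and relative dose intensity come out too high

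*SAP*

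**What the plan says.** SAP 5.1 defines ibrutinib treatment duration in days as the last dose date minus the first dose date plus 1, and adds: "Similarly, treatment duration for dexamethasone will be calculated".

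SAP 5.8 uses that duration, in weeks, twice for dexamethasone. The first use is the denominator of the average dose: "Average dose administered (mg/week) = total cumulative dose administered (mg) / treatment duration (week) for dexamethasone". The second is the total expected dose, which is the same duration multiplied by the "protocol assigned weekly dose (40 mg/week"). It describes the resulting ratio as follows: "Relative dose intensity is defined as the percentage of the total expected dose that was actually administered".

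Protocol 6.3.2 gives the schedule: "Subjects receiving dexamethasone will receive 40 mg orally once per week".

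SAP 5.10 lists a month conversion ("1 month = 30.4375 days") and a year conversion, but none for weeks. SAP 8.6 summarises these parameters by cohort with mean, standard deviation, median and range.

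**The concern.** Last minus first plus one gives the right exposure time when a dose covers one day. A weekly dose covers seven. The formula therefore ends the exposure period on the day of the last dose and ignores the other six days that the dose was meant to cover. Numerator and denominator no longer describe the same period.

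The result is that full adherence does not give 100%. Relative dose intensity is normally read against 100%, so a shortfall from missed or reduced doses can look like near-complete dosing. The error is largest for subjects with few doses, and means and maxima are sensitive to them. Ibrutinib and dexamethasone intensities would also appear under one label while being on different scales.

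**Working it through.** **Inputs**
- Duration in days = last − first + 1, applied to dexamethasone (SAP 5.1).
- Average dose = cumulative mg / duration in weeks; expected dose = duration in weeks × 40 mg; relative dose intensity (RDI) = cumulative / expected (SAP 5.8).
- Schedule: 40 mg once a week (Protocol 6.3.2). A cycle is 28 days (Protocol 6.3.1), so four doses per cycle.
- Assumption: weeks = days/7, unrounded, in line with the fractional month and year conversions in SAP 5.10.

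The documents state no dexamethasone average dose or RDI to reproduce. As a check on the ibrutinib side, 28 daily doses span 28 days and give exactly 100%, so the rule works for the daily drug.

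**Full adherence.** For k on-schedule weekly doses:
- duration = 7(k − 1) + 1 = 7k − 6 days = k − 6/7 weeks
- expected dose = 40(k − 6/7) mg, short by 40 × 6/7 = 34.3 mg whatever k is
- RDI = k/(k − 6/7); average dose = 40k/(k − 6/7) mg/week

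| Doses taken | Days by SAP rule | Average (mg/week) | RDI |
|---|---|---|---|
| 1 | 1 | 280.0 | 700% |
| 2 | 8 | 70.0 | 175% |
| 4 (one cycle) | 22 | 50.9 | 127.3% |
| 8 (two cycles) | 50 | 44.8 | 112.0% |
| 12 (three cycles) | 78 | 43.1 | 107.7% |
| 24 | 162 | 41.5 | 103.7% |

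The correct values are 40 mg/week and 100% in every row. The excess falls below 10% from 10 doses, below 5% from 19 and below 2% from 44.

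**Incomplete dosing**
- One mid-course dose missed in 4 weeks: 120/(40 × 22/7) = 95.5%; true value 3/4 = 75%.
- One missed in 8 weeks: 280/(40 × 50/7) = 98.0%; true value 7/8 = 87.5%.
- Half the doses at 20 mg (true value 75%): over 4 doses 120/(40 × 22/7) = 95.5%; over 8, 240/(40 × 50/7) = 84.0%; over 24, 720/(40 × 162/7) = 77.8%.

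**Effect on a cohort mean (illustration).** One subject with a single dose exceeds 100% by 600 points. That adds 600/18 = 33 points to the mean RDI of an 18-subject cohort, or 600/43 = 14 points with 43 subjects.

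**Last dose off schedule, four full doses**

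| Days from first to last dose | SAP rule | (last − first + 7)/7 |
|---|---|---|
| 20 (one day early) | 160/(40 × 21/7) = 133.3% | 160/(40 × 27/7) = 103.7% |
| 21 (on schedule) | 160/(40 × 22/7) = 127.3% | 160/(40 × 28/7) = 100% |
| 22 (one day late) | 160/(40 × 23/7) = 121.7% | 160/(40 × 29/7) = 96.6% |

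**The case against.** The arithmetic is not open to dispute, but four objections deserve an answer.

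*The size depends on an unstated conversion.* If weeks were rounded up to whole weeks, an exactly on-schedule subject would score 100%. That is true, but the SAP states no such rule and its other conversions are fractional. Rounding up is also fragile: four doses with the last one day early span 21 days, which is 3 weeks, and give 133%. If rounding was intended, the SAP still needs an edit to say so.

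*SAP 5.8 defines expected dose explicitly, so the ratio follows from its own terms.* Formally it does. But the same section describes RDI as the share of the expected dose that was given, and a subject who took every scheduled dose has received all of it. The formula does not deliver that.

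*A missed dose is not hidden, because the bias is a common multiplier.* For a fixed first-to-last span, the relative fall is indeed unchanged: over four weeks RDI drops from 127.3% to 95.5% under the SAP rule and from 100% to 75% under the corrected one, a quarter in both cases. What is wrong is the level. A reader who takes 100% as full dosing sees 95% where the truth is 75%.

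*The consequence is small and covered elsewhere.* This stands in large part. SAP 8.6 separately reports missed doses, "Number of dose reduction for each study drug", and dexamethasone interruptions of 14 or more days. SAP Table 7 adds "TEAEs leading to Dexamethasone dose reduction" and the matching rows for withheld doses and discontinuation. Medians accompany the means, and an RDI far above 100% would show in the range. No test or stage rule uses these summaries.

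**Conclusion.** The concern holds. As written, SAP 5.1 and 5.8 overstate dexamethasone average weekly dose and relative dose intensity by the factor k/(k − 6/7) for k on-schedule doses: 27% at one cycle, 12% at two, 7.7% at three and 3.7% at 24 doses. This rests on taking a week as 7 days without rounding. Calling the effect material up to about three cycles is a judgement; the documents set no threshold.

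How much the trial's tables would move cannot be fixed, because the documents give no dexamethasone durations. The summaries concerned are those for Cohorts 2 and 4, and for subjects in Cohorts 1 and 3 who add dexamethasone. The clinical benefit rate, the stage decisions and the other efficacy results are untouched. Severity is minor.

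**What to change.** In SAP 5.8, for dexamethasone only, add a separately named quantity: exposure weeks = (last dose date − first dose date + 7)/7, with a week equal to 7 days and no rounding. Use it as the denominator of the average weekly dose and as the multiplier in the total expected dose. On-schedule full adherence then gives exactly 40 mg/week and 100% for any number of doses.

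Leave the ibrutinib formulas and the reported treatment duration (SAP 5.1 and 8.6) unchanged. A table footnote should say that average weekly dose uses exposure weeks, because average dose times reported treatment duration will no longer equal the cumulative dose.

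The cost is one line of definition in the SAP, referenced in the two dexamethasone formulas, and one line of code. No dose, schedule or clinical rule changes.

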5.9. Calculation of Laboratory Values

Absolute neutrophil count (ANC):

ANC ($10^9/L$) = (%neutrophils+%bands) × white blood cell / 100, where neutrophils and bands are in percentages and white blood cell is in $10^9/L$.

Estimated creatinine clearance (Clcr) calculated using Cockcroft-Gault (C-G) formula:

$$Clcr(mL/min) = \frac{[140 - Age(years)] \times Weight(kg) \times [0.85 \text{ if Female}]}{72 \times Serum \text{ Creatinine}(mg/dL)}$$

In this calculation, if weight is not measured at the same visit as creatinine, the weight measured prior and closest to the creatinine collection time will be used.

5.10. Other General Definitions

Age:

Age in years will be calculated at the date of informed consent.

Conversions:

- 1 month = 30.4375 days.
- 1 year = 365.25 days.

6. Missing Data Handling

6.1. General Approach

In order to achieve the goal of a well conducted clinical study according to Good Clinical Practice, every effort will be made to collect all data. However, despite best efforts, it may be inevitable that some data may be missing or incomplete. Missing or partial data will be presented in the subject data listing as they are recorded on the case report forms (CRFs).

6.2. Missing and Incomplete Data

6.2.1. Efficacy Variables

No imputation of missing values will be performed for efficacy data unless otherwise specified.

6.2.2. Safety Variables

No imputation of missing values for safety data will be performed.

For missing or partial start and end dates for AEs, medical history, prior therapy and concomitant medication, no imputation will be performed. However, a conservative approach should be taken when performing the related analyses. If the available information is not enough to judge whether an event or a therapy duration has overlapped with study treatment duration, events reported on AE pages will be taken as treatment emergent AEs, events reported on medical history page will be treated as prior medical condition, prior or concomitant therapy will be considered as continuing therapy which started prior to first study treatment.

However, an intermediate imputation of partial dates may be taken in order to calculate the study day for AEs, medical history, prior therapy and concomitant medications. This is just for estimation of the timing of events relative to the study course. All missing or partial dates should remain the same values as they were recorded on the CRFs. The intermediate imputation rules are:

If only day is missing, then the 15th of that month will be used.

If only year is present, then June 30th will be used.

If such imputed date for prior therapies or initial diagnosis is on or after the date of the first dose of study drug, then date of the first dose - 1 will be used. If such imputed date for the start or end of subsequent therapies is before date of last dose of study drug, then date of last

dose of study drug +1 will be assumed. If an imputed start date of prior or subsequent therapy is after the end date, the end date will be used. If an imputed end date of prior or subsequent therapy is before the start date, the start date will be used.

If an imputed AE start date is in the same month and year as the first dose date of study drug but on an earlier date, the first dose date will be used. If an imputed AE start date is in the same month and year as the date of 30 days post the last dose of study drug but on a later date, the date of 30 days post the last dose will be used. If an imputed AE start date is after the AE end date, the AE end date will be used.

If the imputed date is for an AE end date and is after the death date, then the death date will be used, or if the imputed AE end date is before the AE start date, then the AE start date will be used.

7. INTERIM and FINAL ANALYSIS

For each cohort, a futility **interim analysis** will be performed when stage 1 enrollment target met (Cohort 1; 11 subjects, Cohorts 2-4; 18 subjects) and either all enrolled subjects have evaluable response data (ie, completed 6 treatment cycles and the Cycle 7 Day 1 assessments or have discontinued treatment) or the number of clinical benefit responders met stage 2 enrollment expansion criteria (≥ 2 for Cohort 1, ≥ 3 for Cohorts 2-4), whichever occurs earlier. Further enrollment will be halted until the cohort meet stage 2 enrollment expansion criteria. All enrolled subjects will be followed to further assess their responses. Enrollment may resume earlier while waiting for the confirmation of response of the last clinical benefit responder. If a cohort failed to meet stage 2 enrollment expansion criteria when all first stage subjects have evaluable response data, the cohort will be suspended for futility.

The **final analysis** will occur upon study completion.

8. STATISTICAL METHODS

8.1. General Considerations

Unless otherwise stated, continuous variables will be summarized with descriptive statistics (mean, standard error or standard deviation, median, interquartile range, minimum, and maximum). For categorical variables, number and percentage of subjects in each category will be provided.

Time to event or duration of event endpoints will be based on the event date (or censoring date) rather than visit number or visit label.

For by-visit analysis, visit windows will be used to associate assessment with a scheduled visit and will be created in reference to the date of first dose of study drug to assign visit number based on evaluation date. If more than one assessment falls into a given visit window, the one closest to the target date will be used. If two assessments are equally close to the target day, the earlier assessment will be used.

All data collected on the CRFs will be presented in data listings upon request. All statistical analyses will be performed using SAS[®] version 9.2 or higher.

8.2. Analysis of the Conduct of the Study

8.2.1. Subject Enrollment and Disposition

Subject enrollment will be summarized by country, study site and treatment cohort.

The disposition of all enrolled subjects will be summarized by treatment cohort:

- Number of subjects as enrolled, number of subjects as treated, number (%) of subjects in safety and response evaluable populations
- Number (%) of subjects who are still on study treatment.
- Number (%) of subjects with dexamethasone added (Cohorts 1 and 3 only).
- Number (%) of subjects who discontinued the study treatment and reason for discontinuation
- Number (%) of subjects who exited the study and reason for study exit
- Descriptive statistics for time on study; time on study is defined in the same way as overall survival with reversed censoring, i.e., subjects who died will be censored at death date. The Kaplan-Meier method will be used to estimate the median time on study.

The percentages will be based on the number of subjects treated.

8.2.2. Protocol Deviations

Subjects with important protocol deviations (IPDs) will be identified and documented by clinical team.

8.3. Study Periods

The whole study period is defined as the period of time from the date of the first dose of study drug until the end of the study.

The monotherapy period (Cohorts 1 and 3 only) is defined as the period of time from the date of the first dose of ibrutinib through the day before the addition of dexamethasone, or the day before initiation of any subsequent anti-myeloma therapy, whichever occurs first.

8.4. Demography and Baseline Disease Characteristics

The following demographic and baseline disease characteristics will be summarized for the all treated population by treatment cohort.

- Demographics: Sex, age (continuous and grouped as <65, ≥65, <70, ≥70, <75, ≥75 years), race, and ethnicity
- Baseline and disease characteristics:
 - Weight and height
 - ECOG performance status (0, 1)
 - Creatinine, estimated creatinine clearance rate (continuous and grouped as < 30, 30-<60, ≥ 60 mL/min)
 - Hematologic abnormalities (hemoglobin [Hgb] < 10 g/dL, platelets < 100×10⁹/L, ANC < 1×10⁹/L)
 - Hemoglobin, platelet counts and ANC
 - Time since initial diagnosis (continuous and grouped as <3, ≥3 years)
 - Disease status (relapsed, relapsed and refractory)
 - Serum β₂-microglobulin (continuous and grouped as <3.5, ≥3.5 - <5.5, ≥5.5 mg/L)
 - Serum albumin (continuous and grouped as <3.5, ≥3.5 g/dL)
 - Disease stage (I, II, III) at baseline per International Staging System (see Table 2)
 - Immunoglobulin heavy chain class (e.g. A, G, M), immunoglobulin light chain class (κ, λ)
 - Measurable disease (SPEP only, UPEP only, SPEP and UPEP, sFLC only)
 - Bone marrow plasma cell percentage
 - Cytogenetic/FISH prognostic markers [e.g. del(17p), del(13q14), t(4;14), t(11;14)]
- Prior cancer-related therapies:
 - Prior radiotherapy (yes, no), prior surgery (yes, no), prior systemic therapy (yes, no)
 - Number of prior systemic therapies (continuous and grouped as 2-3, ≥4)

-
- Type of prior systemic therapies: lenalidomide, thalidomide, pomalidomide, bortezomib, carfilzomib, alkylator (melphalan, cyclophosphamide), doxorubicin, corticosteroid (dexamethasone, prednisone), fludarabine, vincristine, etc.
 - Type of bone marrow or stem cell transplant: autologous, allogeneic
 - Refractory to last line of therapy
 - Refractory to prior immunomodulatory drugs: lenalidomide, thalidomide, pomalidomide
 - Refractory to prior proteasome inhibitors: bortezomib, carfilzomib
 - Refractory to prior immunomodulatory drugs and proteasome inhibitors (i.e. refractory to at least one prior immunomodulatory drug and at least one prior proteasome inhibitor)
 - Last prior treatment [(no PI/IMiD) vs. (PI or IMiD) vs. (PI and IMiD)]
 - Last prior treatment included PI
 - Last prior treatment included IMiD

